5.7 Contraception and Pregnancy

5.7.1 Contraception

Pembrolizumab may have adverse effects on a fetus in utero. Furthermore, it is not known if Pembrolizumab has transient adverse effects on the composition of sperm. Non-pregnant, non-breast-feeding women may be enrolled if they are willing to use 2 methods of birth control or are considered highly unlikely to conceive. Highly unlikely to conceive is defined as 1) surgically sterilized, or 2) postmenopausal (a woman who is \geq 45 years of age and has not had menses for greater than 1 year will be considered postmenopausal), or 3) not heterosexually active for the duration of the study. The two birth control methods can be either two barrier methods or a barrier method plus a hormonal method to prevent pregnancy. Subjects should start using birth control from study Visit 1 throughout the study period up to 120 days after the last dose of study therapy.

The following are considered adequate barrier methods of contraception: diaphragm, condom (by the partner), copper intrauterine device, sponge, or spermicide. Appropriate hormonal contraceptives will include any registered and marketed contraceptive agent that contains an estrogen and/or a progestational agent (including oral, subcutaneous, intrauterine, or intramuscular agents).

Subjects should be informed that taking the study medication may involve unknown risks to the fetus (unborn baby) if pregnancy were to occur during the study. In order to participate in the study they must adhere to the contraception requirement for the duration of the study and during the follow-up period. If there is any question that a subject will not reliably comply with the requirements for contraception, that subject should not be entered into the study.

5.7.2 Use in Pregnancy

If a subject inadvertently becomes pregnant while on treatment with Pembrolizumab, the subject will immediately be removed from the study. The site will contact the subject at least monthly and document the subject's status until the pregnancy has been completed or terminated. The outcome of the pregnancy will be reported to the Sponsor without delay and within 24 hours if the outcome is a serious adverse experience (e.g., death, abortion, congenital anomaly, or other disabling or life-threatening complication to the mother or newborn). The study investigator will make every effort to obtain permission to follow the outcome of the pregnancy and report the condition of the fetus or newborn to the Sponsor. If a male subject impregnates his female partner the study personnel at the site must be informed immediately and the pregnancy reported to the Sponsor and followed as described above and in Section 8.2.2.

5.7.3 Use in Nursing Women

It is unknown whether Pembrolizumab is excreted in human milk. Since many drugs are excreted in human milk, and because of the potential for serious adverse reactions in the nursing infant, subjects who are breast-feeding are not eligible for enrollment.

5.8 Subject Withdrawal/Discontinuation Criteria

Subjects may withdraw consent at any time for any reason or be dropped from the trial at the discretion of the investigator should any untoward effect occur. In addition, a subject may be withdrawn by the investigator or the Sponsor if enrollment into the trial is inappropriate, the trial plan is violated, or for administrative and/or other safety reasons.

A subject must be discontinued from the trial for any of the following reasons:

- Withdrawal of consent.
- Confirmed radiographic disease progression

Note: A subject may be granted an exception to continue on treatment with confirmed radiographic progression if clinically stable or clinically improved, as consistent with irRC.

- Unacceptable adverse experiences or toxicities
- Intercurrent illness that prevents further administration of treatment
- Investigator's decision to withdraw the subject
- Confirmed positive serum pregnancy test and unwillingness to abort pregnancy
- Noncompliance with trial treatment or procedure requirements
- Loss to follow-up
- Completion of 17 cycles (about 12 months) of treatment with Pembrolizumab
- Other Administrative reasons

The End of Treatment and Follow-up visit procedures are listed in Section 7 (Protocol Flow Chart). After the end of treatment, each subject will be followed for 30 days for adverse event monitoring (serious adverse events will be collected for 90 days after the end of treatment). Subjects who discontinue for reasons other than progressive disease will have post-treatment follow-up for disease status until disease progression, initiation of non-study cancer treatment, withdrawal of consent or loss to follow-up. After documented disease progression each, subject will be followed by telephone or chart review for overall survival until death, withdrawal of consent, or the end of the study, whichever occurs first. All subsequent therapies will be recorded, if feasible.

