Treatment with Pembrolizumab will continue for 17 cycles (about 12 months) in the absence of (1) documented disease progression, (2) unacceptable adverse event(s), (3) intercurrent illness that prevents further administration of treatment, (4) investigator's decision to withdraw the subject, (5) subject withdrawal of consent, (6) pregnancy of the subject, (7) noncompliance with trial treatment or procedure requirements, (8) institution of alternative systemic treatment, or (9) other administrative reasons. After the end of treatment, each subject will be followed for a minimum of 30 days for adverse event monitoring (serious adverse events will be collected for up to 90 days after the end of treatment). Subjects will have post-treatment follow-up for disease status until one of the following events: (1) disease progression; (2) initiation of non-study cancer treatment; (3) withdrawal of study consent; (4) loss to follow-up or (5) death. In addition, survival status beyond the establishment of PD or initiation of subsequent therapies will be documented.

The primary objective of the trial includes determination of PFS per RECIST 1.1. Secondary objectives include OS and safety/toxicity determination as assessed by a variety of parameters of adverse events (AEs), including incidence and time to first Grade 3-5 AE. Pre-specified adverse events of clinical interest during the Pembrolizumab phase include the following events: 1) Grade \geq 3 diarrhea 2) Grade \geq 2 colitis, 3) Grade \geq 2 pneumonitis, 4) Grade \geq 3 hypo- or hyperthyroidism, 5) Grade \geq 2 hypophysitis, 6) Grade \geq 2 uveitis, and 7) Grade \geq 2 nephritis. Participation in this trial will encourage supplying tumor tissue from either a newly obtained formalin-fixed specimen (preferred) or an older formalin-fixed, paraffin-embedded specimen, from locations not radiated prior to biopsy. The specimen will be evaluated at a central laboratory facility for expression status of PD-L1 in a retrospective manner. Eligibility for the trial will not be dependent upon PD-L1 expression status, but the sponsor may amend the trial in the future if new data arise regarding the predictive value of PD-L1 expression. Any patient enrolled on the study prior to such an amendment, however, will remain on study.

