7 TRIAL FLOW CHART

7.1 Trial Flow Chart

Table 6: Study procedures by visit

Trial Period:	Screening Phase	Proton Reirradiation +/- Chemo-therapy	Pembrolizumab Treatment Cycles*										Post-Treatment	
Treatment Cycle /Title:	Screening	Reirradiation	1/9	2/10	3/11	4/12	5/13	6/14	7/15	8/16	17	Safety Follow-up	Follow Up Visits	
Scheduling Window (Days):	-28 to -1	Daily protons for 3-8 weeks	± 3	± 3	± 3	± 3	± 3	± 3	± 3	± 3	At last treatment	30 days post tx/discon	Every 3 months for 2 yrs	
Administrative Procedures														
Informed Consent	X													
Inclusion/Exclusion Criteria	X													
Demographics and Medical History	X													
Prior and Concomitant Medication Review	X	X	X	X	X	X	X	X	X	X	X			
Trial Treatment Administration			X	X	X	X	X	X	X	X	X			
Post-study anticancer therapy status												X		X
Survival Status		X	X	X	X	X	X	X	X	X	X	X		X
Clinical Procedures/Assessments														
Review Adverse Events**			X	X	X	X	X	X	X	X	X	X		X
Full Physical Examination	X					X				X		X		X
Directed Physical Examination		X	X	X	X		X	X	X		X			
Vital Signs and Weight	X	X	X	X	X	X	X	X	X	X	X	X		X
ECOG Performance Status	X	X	X	X	X	X	X	X	X	X	X	X		X
Laboratory Procedures/Assessments: analysis performed by LOCAL laboratory														
Pregnancy Test – Urine or Serum β-HCG	X													
PT/INR and aPTT	X													
CBC with Differential	X			X	X	X	X	X	X	X	X	X		X
Comprehensive Serum Chemistry	X			X	X	X	X	X	X	X	X	X		X

Phase II Pembrolizumab Reirradiation

Trial Period:	Screening Phase	Proton Reirradiation +/- Chemo-therapy	Pembrolizumab Treatment Cycles*										Post-Treatment	
			Pembrolizumab Treatment Cycles*										Post-Treatment	
Treatment Cycle /Title:	Screening	Reirradiation	1/9	2/10	3/11	4/12	5/13	6/14	7/15	8/16	17		Safety Follow-up	Follow Up Visits
Scheduling Window (Days):	-28 to -1	Daily protons for 3-8 weeks	± 3	± 3	± 3	± 3	± 3	± 3	± 3	± 3	At last treatment	30 days post tx/discon	Every 3 months for 2 yrs	
Urinalysis	X				X				X			X		
T3, FT4 and TSH	X			X			X			X		X		
Efficacy Measurements														
Tumor Imaging	X***	X	X				X, X				X			X
Tumor Biopsies/Archival Tissue Collection/Correlative Blood Studies														
Archival or Newly Obtained Tissue Collection (optional)	X													
Correlative Studies Blood Collection	X			X				X			X	X	X	

For the Pembrolizumab phase, we will report all treatment-related toxicities.

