8.1.3.1 Laboratory Safety Evaluations (Hematology, Chemistry and Urinalysis)

Laboratory tests for hematology, chemistry, urinalysis, and others are specified in Table 7. The total amount of blood/tissue to be drawn/collected over the course of the trial (from pre-trial of Pembrolizumab to post-trial of Pembrolizumab visits), including approximate blood/tissue volumes drawn/collected by visit and by sample type per subject may vary depending upon clinical course of the subject and length of time on trial. Blood testing done during the reirradiation + -chemo phase will be done per standard of care.

Table 7: Laboratory Tests

Hematology	Chemistry	Urinalysis	Other
Hematocrit	Albumin	Blood	Serum β -human chorionic gonadotropin†
Hemoglobin	Alkaline phosphatase	Glucose	(β -hCG)†
Platelet count	Alanine aminotransferase (ALT)	Protein	PT (INR)
WBC (total and differential)	Aspartate aminotransferase (AST)	Specific gravity	aPTT
Red Blood Cell Count		Microscopic exam (If abnormal)	Total triiodothyronine (T3)
Absolute Neutrophil Count	Carbon Dioxide (CO_2 or bicarbonate)	results are noted	Free tyroxine (T4)
	Calcium	Urine pregnancy test †	Thyroid stimulating hormone (TSH)
	Chloride		
	Glucose		Blood for correlative studies
	Potassium		
	Sodium		
	Total Bilirubin		
	Direct Bilirubin (If total bilirubin is elevated above the upper limit of normal)		
	Total protein		
	Blood Urea Nitrogen		

† Perform on women of childbearing potential only. If urine pregnancy results cannot be confirmed as negative, a serum pregnancy test will be required.

After Cycle 1, pre-dose laboratory procedures can be conducted up to 72 hours prior to dosing. Results must be reviewed by the investigator or qualified designee and found to be acceptable prior to each dose of Pembrolizumab.

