8.1.5.1 Screening

Visit requirements are outlined in Section 7.0 - Trial Flow Chart.

Prior to treatment initiation of Pembrolizumab, potential subjects will be evaluated to determine that they fulfill the entry requirements. Screening procedures may be repeated.

Written informed consent must be obtained prior to performing any protocol specific procedure.

Results of a test performed prior to the subject signing consent as part of routine clinical management are acceptable in lieu of a screening test if performed within the specified time frame. Screening procedures are to be completed within 42 days prior to the first dose of trial treatment of Pembrolizumab except for the following:

- Laboratory tests are to be performed within 10 days prior to the first dose of trial treatment of Pembrolizumab.
- For women of reproductive potential, a urine pregnancy test will be performed within 72 hours prior to first dose of trial treatment. If urine pregnancy results cannot be confirmed as negative, a serum pregnancy test, performed by the local study site laboratory, will be required.

Subjects may be rescreened after initially failing to meet the inclusion/exclusion criteria. Results from assessments performed during the initial screening period are acceptable in lieu of a repeating a screening test if performed within the specified time frame and the results meet the inclusion/exclusion criteria.

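### The pregnancy item in the Section 5.8 mandatory discontinuation list depends on unwillingness to abort, which makes it narrower than the unconditional rule in Section 5.7.2 and out of line with Section 3.1

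*Combined protocol and SAP*

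**What the plan says.** Three places in the combined protocol and SAP deal with a subject who becomes pregnant.

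- **Section 5.8 (Subject Withdrawal/Discontinuation Criteria)** gives a list of reasons, any one of which makes discontinuation from the trial obligatory. Its only pregnancy entry is "Confirmed positive serum pregnancy test and unwillingness to abort pregnancy".
- **Section 5.7.2 (Use in Pregnancy)** states: "If a subject inadvertently becomes pregnant while on treatment with Pembrolizumab, the subject will immediately be removed from the study". It then requires at least monthly contact until the pregnancy ends, whether by completion or termination, and it names abortion among the outcomes reportable within 24 hours.
- **Section 3.1 (General Design)** continues pembrolizumab only while none of nine listed reasons is present. One of them is "6) pregnancy of the subject", with nothing added.

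The reason for the rule is in Section 5.7.1: "Pembrolizumab may have adverse effects on a fetus in utero".

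On testing, the footnote to Table 7 in Section 8.1.3.1 says: "If urine pregnancy results cannot be confirmed as negative, a serum pregnancy test will be required".

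**The concern.** Section 5.8 is where staff would naturally look to see whether a subject has to come off the trial. On pregnancy it holds the narrowest text in the protocol. The word joining its two parts makes each of them necessary, and neither part appears in 5.7.2 or 3.1.

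The abortion part is the more serious. It makes a protective rule depend on what the participant intends to do about her pregnancy. That intention has no bearing on whether the fetus is exposed at the next infusion. A coordinator working from the 5.8 list alone would find no required discontinuation for a pregnant subject who says she is willing to abort.

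What is at stake is participant safety and the clarity of an ethically sensitive instruction. No estimate or test is involved.

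**Working it through.** No arithmetic applies. The check sets the rules side by side and asks what each one requires.

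**Step 1. Scope.** Sections 5.7.2 and 5.8 both govern removal from the study or trial. Section 3.1 governs whether pembrolizumab continues. The direct inconsistency is therefore between 5.8 and 5.7.2. Section 3.1 supports the unconditional reading as far as drug treatment is concerned.

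**Step 2. Cases.** Take a subject on pembrolizumab who is pregnant. Section 5.8 adds two yes/no conditions, which gives 2 × 2 = 4 cases.

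| Positive serum test confirmed? | Unwilling to abort? | 5.7.2: remove from study | 3.1: stop pembrolizumab | 5.8 pregnancy item met |
|---|---|---|---|---|
| Yes | Yes | Yes | Yes | Yes |
| Yes | No | Yes | Yes | **No** |
| No | Yes | Yes | Yes | **No** |
| No | No | Yes | Yes | **No** |

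The sections agree only in the first row. This counts logical cases and says nothing about how often each would occur.

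**Step 3. Which rows matter.** The second row carries the point. Pregnancy is fully confirmed, 5.7.2 requires removal, and the 5.8 item is not met solely because the subject is willing to abort.

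The third and fourth rows matter less. The Table 7 footnote calls for a serum test whenever a urine result cannot be confirmed as negative, and its wording does not confine this to screening. A positive urine test should therefore lead to serum confirmation. What remains is the interval before that result, or a pregnancy established by other means.

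**Step 4. Does anything else in 5.8 close the gap?** The list also includes the investigator's decision, and the opening paragraph allows withdrawal on safety grounds. Both are discretionary. Noncompliance need not apply, because 5.7.2 itself contemplates an inadvertent pregnancy. None of these restores an unconditional rule.

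**Step 5. Does any section set precedence?** No section refers to the discrepancy or ranks one rule above another.

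**Step 6. Effect on the analysis.** Under Section 5.9 a subject is evaluable, and not replaced, after one dose of proton reirradiation. Section 4.4.2 follows all patients for PFS and OS. The wording of the 5.8 item enters neither the 41-patient sample size nor the power statement in Section 9.4.

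**The case against.** The strongest reply is that nothing forces a site into an unsafe act. Section 5.8 lists reasons that are each sufficient. It does not say that a subject outside the list stays on treatment. All the rules can be obeyed together, because removing every pregnant subject under 5.7.2 breaches nothing in 5.8. Section 5.7.2 has its own heading, comes just before 5.8, and already covers the subject who terminates: she is removed first and then followed. Harm requires someone to use the 5.8 list alone. All of this stands, and it limits how serious the point is. It does not make the 5.8 item correct, since a mandatory list should not state the rule more narrowly than the section devoted to it.

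Some stronger readings are tempting but are not supported:

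- **That 5.8 lets a subject remain on pembrolizumab if she ends the pregnancy.** A reader might infer this from the wording. Section 5.8 grants no such permission, and 5.7.2 removes her whatever she decides.
- **That the protocol contains three competing rules.** Sections 3.1 and 5.7.2 do not disagree. They differ in scope, and 5.8 is the outlier.
- **That a subject found pregnant during reirradiation could go on to start pembrolizumab.** Section 8.1.5.1 guards that step: "Prior to treatment initiation of Pembrolizumab, potential subjects will be evaluated to determine that they fulfill the entry requirements". For women of reproductive potential, it adds that "a urine pregnancy test will be performed within 72 hours prior to first dose of trial treatment". Pregnancy is an exclusion in Section 4.2, and Section 4.4.1 lists failure of the eligibility criteria as a reason for withdrawal.
- **That the testing schedule measures the defect.** Table 6 has a row "Pregnancy Test – Urine or Serum β-HCG", and a reader might count the visits at which it is marked, or the length of treatment. Detection under 5.7.2 and 3.1 depends on the same schedule, so it does not set 5.8 apart. The table's layout was also disturbed in extraction, and the proposed edit leaves testing unchanged.

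**Conclusion.** The point holds in limited form. The pregnancy item in 5.8 is wrong as written, because it makes mandatory discontinuation depend on unwillingness to abort while 5.7.2 requires immediate removal for pregnancy itself and 3.1 stops the drug for pregnancy alone. The serum-test condition is a secondary mismatch, mostly covered by the Table 7 footnote.

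The practical size is small. Pregnant patients are excluded, contraception is required, and a site that applies 5.7.2 takes the safe action. The event should be rare among 41 patients, but the documents give no figure from which a rate could be derived. PFS, sample size and power are untouched. The item should still be corrected, because women of reproductive potential may enrol under the contraception requirement and the mandatory list should give the right instruction if the event occurs.

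The conclusion rests on reading the two parts of the 5.8 item as jointly necessary, which is the plain sense of the sentence, and on the absence of any text that reconciles the sections. It rests on intact prose in 3.1, 5.7.2 and 5.8 and not on any damaged table.

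**What to change.** In Section 5.8, replace the current entry with: *Pregnancy of the subject (see Section 5.7.2)*. This deletes the abortion condition and the serum-only trigger together, and it brings 5.8 into line with 5.7.2 and 3.1.

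The cost is one list item in an amendment. Visits, scheduled tests, sample size and the analysis do not change.

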5.9 Subject Replacement Strategy

Subjects who receive at least 1 dose of proton reirradiation will be considered evaluable and will not be replaced.

5.10 Clinical Criteria for Early Trial Termination

Early trial termination will be the result of the criteria specified below:

1. Quality or quantity of data recording is inaccurate or incomplete
2. Poor adherence to protocol and regulatory requirements
3. Incidence or severity of adverse drug reaction in this or other studies indicates a potential health hazard to subjects
4. Plans to modify or discontinue the development of the study drug

In the event of Merck decision to no longer supply study drug, ample notification will be provided so that appropriate adjustments to subject treatment can be made.

6 Labeling, Packaging, Storage and Return of Clinical Supplies

6.1 Labeling

Clinical supplies will be affixed with a clinical label in accordance with regulatory requirements. This trial is open-label; therefore, the subject, the trial site personnel, the Sponsor and/or designee are not blinded to treatment. Drug identity (name, strength) is included in the label text; random code/disclosure envelopes or lists are not provided.

6.2 Storage and Handling Requirements

Clinical supplies must be stored in a secure, limited-access location under the storage conditions specified on the label. They will be stored in the Investigational Drug Pharmacy as part of the Abramson Cancer Center.

Receipt and dispensing of trial medication must be recorded by an authorized person at the trial site.

Clinical supplies may not be used for any purpose other than that stated in the protocol.

6.3 Returns and Reconciliation

The investigator is responsible for keeping accurate records of the clinical supplies received from Merck or designee, the amount dispensed to and returned by the subjects and the amount remaining at the conclusion of the trial.

Upon completion or termination of the study, all unused and/or partially used investigational product will be destroyed at the site per institutional policy. It is the Investigator's responsibility to arrange for disposal of all empty containers, provided that procedures for proper disposal have been established according to applicable federal, state, local and institutional guidelines and procedures, and provided that appropriate records of disposal are kept.

7 TRIAL FLOW CHART

7.1 Trial Flow Chart

Table 6: Study procedures by visit

Trial Period:	Screening Phase	Proton Reirradiation +/- Chemo-therapy	Pembrolizumab Treatment Cycles*										Post-Treatment	
Treatment Cycle /Title:	Screening	Reirradiation	1/9	2/10	3/11	4/12	5/13	6/14	7/15	8/16	17	Safety Follow-up	Follow Up Visits	
Scheduling Window (Days):	-28 to -1	Daily protons for 3-8 weeks	± 3	± 3	± 3	± 3	± 3	± 3	± 3	± 3	At last treatment	30 days post tx/discon	Every 3 months for 2 yrs	
Administrative Procedures														
Informed Consent	X													
Inclusion/Exclusion Criteria	X													
Demographics and Medical History	X													
Prior and Concomitant Medication Review	X	X	X	X	X	X	X	X	X	X	X			
Trial Treatment Administration			X	X	X	X	X	X	X	X	X			
Post-study anticancer therapy status												X		X
Survival Status		X	X	X	X	X	X	X	X	X	X	X		X
Clinical Procedures/Assessments														
Review Adverse Events**			X	X	X	X	X	X	X	X	X	X		X
Full Physical Examination	X					X				X		X		X
Directed Physical Examination		X	X	X	X		X	X	X		X			
Vital Signs and Weight	X	X	X	X	X	X	X	X	X	X	X	X		X
ECOG Performance Status	X	X	X	X	X	X	X	X	X	X	X	X		X
Laboratory Procedures/Assessments: analysis performed by LOCAL laboratory														
Pregnancy Test – Urine or Serum β-HCG	X													
PT/INR and aPTT	X													
CBC with Differential	X			X	X	X	X	X	X	X	X	X		X
Comprehensive Serum Chemistry	X			X	X	X	X	X	X	X	X	X		X

Phase II Pembrolizumab Reirradiation

Trial Period:	Screening Phase	Proton Reirradiation +/- Chemo-therapy	Pembrolizumab Treatment Cycles*										Post-Treatment	
			Pembrolizumab Treatment Cycles*										Post-Treatment	
Treatment Cycle /Title:	Screening	Reirradiation	1/9	2/10	3/11	4/12	5/13	6/14	7/15	8/16	17		Safety Follow-up	Follow Up Visits
Scheduling Window (Days):	-28 to -1	Daily protons for 3-8 weeks	± 3	± 3	± 3	± 3	± 3	± 3	± 3	± 3	At last treatment	30 days post tx/discon	Every 3 months for 2 yrs	
Urinalysis	X				X				X			X		
T3, FT4 and TSH	X			X			X			X		X		
Efficacy Measurements														
Tumor Imaging	X***	X	X				X, X				X			X
Tumor Biopsies/Archival Tissue Collection/Correlative Blood Studies														
Archival or Newly Obtained Tissue Collection (optional)	X													
Correlative Studies Blood Collection	X			X				X			X	X	X	

For the Pembrolizumab phase, we will report all treatment-related toxicities.

*The Pre-Screening visit and Main Study Screening visit may be combined to one Study Screening visit in some patient circumstances

*Cycles 9-17 are to be repeated using same trial flow chart as cycles 1-8

**AEs will be monitored for one year following treatment for patients who complete all 17 cycles of Pembrolizumab. AEs will be followed for 30 days, and SAEs for 90 days, for patients who discontinue the study early for any reason.

***Baseline tumor imaging may occur up to 42 days before starting standard of care treatment

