5.2 Treatment Regimen

Patients will be treated with reirradiation with or without standard concurrent chemotherapy to all gross disease with proton beam therapy. The intended radiation dose should be at least 60 Gy of reirradiation in 1.8-2.0 Gy fractions with or without concurrent chemotherapy or in 4.0 Gy fractions without chemotherapy, at the provider's discretion. This corresponds to daily fractionated radiation over a period of approximately 3-8 weeks. The decision to use concurrent chemotherapy, and which regimen to utilize, are left to the discretion of the treating oncologist. The chemotherapy regimen and doses will be recorded in the patient record.

Pembrolizumab will be started 4 to 12 weeks after completion of reirradiation. Pembrolizumab will be given at a dose of 200 mg intravenously approximately every 21 days for 17 cycles (about 12 months) if there is no evidence of progressive disease or intolerable side effects.

Dose Modifications (Escalation/Titration/Other)

Adverse events (both non-serious and serious) associated with pembrolizumab exposure may represent an immunologic etiology. These adverse events may occur shortly after the first dose or several months after the last dose of treatment. Pembrolizumab must be withheld for drug-related toxicities and severe or life-threatening AEs as per 3 below. See Section 5.6 for supportive care guidelines, including use of corticosteroids.

Table 1: Dose Modification Guidelines for Drug-Related Adverse Events

Toxicity	Hold Treatment For Grade	Timing for Restarting Treatment	Treatment Discontinuation
Diarrhea/Colitis	2-3	Toxicity resolves to Grade 0-1	Toxicity does not resolve within 12 weeks of last dose or inability to reduce corticosteroid to 10 mg or less of prednisone or equivalent per day within 12 weeks
	4	Permanently discontinue	Permanently discontinue
AST, ALT, or Increased Bilirubin	2	Toxicity resolves to Grade 0-1	Toxicity does not resolve within 12 weeks of last dose
	3-4	Permanently discontinue (see exception below) ^a	Permanently discontinue
Type 1 diabetes mellitus (if new onset) or Hyperglycemia	T1DM or 3-4	Hold pembrolizumab for new onset Type 1 diabetes mellitus or Grade 3-4 hyperglycemia associated with evidence of beta cell failure	Resume pembrolizumab when patients are clinically and metabolically stable

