8.2 Assessing and Recording Adverse Events

An adverse event is defined as any untoward medical occurrence in a patient or clinical investigation subject administered a pharmaceutical product and which does not necessarily have to have a causal relationship with this treatment. An adverse event can therefore be any unfavorable and unintended sign (including an abnormal laboratory finding, for example), symptom, or disease temporally associated with the use of a medicinal product or protocol-specified procedure, whether or not considered related to the medicinal product or protocol-specified procedure. Any worsening (i.e., any clinically significant adverse change in frequency and/or intensity) of a preexisting condition that is temporally associated with the use of the Merck's product, is also an adverse event.

Merck product includes any pharmaceutical product, biological product, device, diagnostic agent or protocol-specified procedure, whether investigational (including placebo or active comparator medication) or marketed, manufactured by, licensed by, provided by or distributed by Merck for human use.

Phase II Pembrolizumab Reirradiation

Adverse events may occur during the course of the use of Merck product in clinical trials or within the follow-up period specified by the protocol, or prescribed in clinical practice, from overdose (whether accidental or intentional), from abuse and from withdrawal.

All adverse events will be recorded from beginning with cycle 1 of Pembrolizumab through 30 days following cessation of treatment and at each examination on the Adverse Event case report forms/worksheets. Laboratory AE's will also start being recorded beginning with cycle 1 of Pembrolizumab. The reporting timeframe for adverse events meeting any serious criteria is described in section 8.2.3.1.

Applicable reporting to DSMC will occur as follows:

On-Site subjects (this includes any subjects enrolled at other sites on an in-house study)

1. All grade 3 or higher events (AE or SAE) within five business days of knowledge.
2. All unexpected deaths within 24 hours of knowledge.
3. All others deaths within 30 days of knowledge. Deaths of subjects off-study for greater than 30 days from the last study treatment/intervention are not reportable with the following exceptions:

Study Exceptions the CTSRMC will not Approve:

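### How long new adverse events are collected after pembrolizumab depends on whether the patient completed 17 cycles, and the sections that set the window disagree

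*Combined protocol and SAP*

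**What the plan says.** Five places in the combined protocol and SAP bear on the post-treatment window.

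- **Section 7.1, Table 6, footnote to the adverse event review row.** For completers: "AEs will be monitored for one year following treatment for patients who complete all 17 cycles of Pembrolizumab". For the rest: "AEs will be followed for 30 days, and SAEs for 90 days, for patients who discontinue the study early for any reason". I read the second group as everyone who stops pembrolizumab before cycle 17.
- **Section 5.8.** No split by completion: "After the end of treatment, each subject will be followed for 30 days for adverse event monitoring". Serious adverse events (SAEs) are collected for 90 days.
- **Section 8.2.** No split, but an open-ended tail: recording runs "through 30 days following cessation of treatment and at each examination on the Adverse Event case report forms/worksheets".
- **Section 8.1.2.1.** AEs are recorded after pembrolizumab starts and during follow-up, with no limit in days.
- **Section 3.1.** "each subject will be followed for a minimum of 30 days for adverse event monitoring", with SAEs collected for up to 90 days.

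On the timing of immune toxicity, section 5.2 says: "These adverse events may occur shortly after the first dose or several months after the last dose of treatment". Section 5.6.1.1 says the same of immune-related events. Section 3.1 describes the safety objective as "including incidence and time to first Grade 3-5 AE", among other parameters, and names events of interest that include pneumonitis of Grade 2 or higher. Section 9.4 says only that toxicities will be graded, categorized and tabled.

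**The concern.** Completing 17 cycles is known only after treatment has begun, and it is related to progression and tolerance. A collection window tied to it means that the same new event, on the same day after the last dose, is recorded in one patient and not in another. A new, non-serious Grade 2 pneumonitis on day 45 would be captured in a completer and missed in a patient who stopped early, although section 3.1 names that event.

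The tabulated incidence would then be a mixture whose meaning depends on how many patients completed. Section 9 specifies no common window and no time-at-risk method to correct this. Time to first Grade 3-5 AE would have no settled end of observation, because the sections disagree on when collection stops. Section 9.4 also undertakes to report all treatment-related toxicities of the pembrolizumab phase. A 30-day window cannot deliver that if events arise months after the last dose.

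**Working it through.** The plan states no figure for this point, so there is none to reproduce. The check compares the windows and then asks how many patients each would cover.

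**1. Do the passages agree?** Section 5.8 (30/90 days for each subject) does not match the footnote's year for completers. Section 8.2 can be read as stopping at 30 days or as continuing at every later examination. Section 8.1.2.1 sets no stop. Section 3.1 states a minimum, which is compatible with the footnote but does not settle the rule. The AE review mark at the follow-up visits in Table 6 does not settle it either, because that row carries the footnote marker.

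**2. Size of the difference under the footnote.**
- AEs: 365 / 30 = 12.2.
- SAEs: 365 / 90 = 4.1, taking the completers' year to include serious events. It is therefore an upper figure.

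**3. How many patients would have the short window?** Inputs: 17 doses at 21-day intervals (section 5.2); exponential PFS with a median of 10 months, or 6 months for the historical control (section 9.4); 35 patients starting pembrolizumab (section 9.4).
- First to last dose: 16 x 21 = 336 days; 336 / 30.4375 = 11.04 months.
- Share still progression-free at cycle 17: S = 2^(-11.04 / median). The constant hazard allows the clock to start at cycle 1.
- Median 10 months: S = 0.465, or 35 x 0.465 = 16.3 patients. Short window: 53.5%.
- Median 6 months: S = 0.279, or 35 x 0.279 = 9.8 patients. Short window: 72.1%.

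Stops for toxicity or other reasons would raise these shares. The section 5.8 exception allowing some patients to continue after progression would lower them.

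**4. How much late toxicity could each window catch?** The documents give no onset distribution. As an assumption, let late events arise exponentially after the last dose with median m. The share captured by day t is 1 - 2^(-(t / 30.4375) / m).

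| Assumed m (months) | 30 days | 90 days | 365 days |
|---|---|---|---|
| 1 | 50% | 87% | 100% |
| 2 | 29% | 64% | 98% |
| 3 | 20% | 50% | 94% |
| 6 | 11% | 29% | 75% |

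This table shows only how sensitive capture is to the window. It is not an estimate of toxicity in this trial.

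**The case against.** The gap is narrower than the footnote alone suggests. Serious events are collected for 90 days in early stoppers. Events already open are not dropped: section 8.1.5.6 follows events above Grade 1 to Grade 0-1 or new therapy, and section 4.4.2 follows patients taken off study for toxicity to resolution or stabilization. Section 8.2.3.2 reports events of clinical interest for up to 90 days. The trial has one arm, so no between-arm safety comparison is distorted. After progression many patients may start other treatment, which makes late events hard to attribute.

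Most of this stands, and it confines the point to new-onset events. It does not close the gap. New Grade 2 events, and some Grade 3 events, need not meet the seriousness criteria in section 8.2.3.1. The list in section 8.2.3.2 names overdose and a combined liver-test elevation, not the section 3.1 events. Even if those were read into it, that window falls to 30 days when new anticancer therapy starts. The attribution difficulty is a reason to flag events after new therapy, not a reason to let the window depend on completion.

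A reader might also infer that late toxicity is missed where it is most likely. The documents do not support that. They give no late-toxicity rates by group, early stoppers include patients who stop for progression, and completers have the greatest exposure.

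**Conclusion.** The point holds as a contradiction over the AE window and as a source of unequal follow-up for new-onset events. The day counts come directly from the text. The 53.5% to 72.1% share with the short window is illustrative and rests on the exponential model and the assumptions in the working.

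Three further inferences should not be drawn.

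- **That stopping for toxicity censors the Grade 3-5 endpoint.** A patient who stops for such an event has already been counted. At most, the argument reaches those who stop for lower-grade toxicity, progression or other reasons.
- **That the regimen is made to look safer.** This is true only against a one-year window for everyone, which the plan does not promise. Against the uniform 30/90-day rule in section 5.8, the footnote adds events.
- **That observation differs as 701 days (336 + 365) against 51 days (21 + 30, for a patient who stops after dose 2).** That contrast includes time on treatment, which the footnote does not cause. It would still be 701 against 386 days (21 + 365) if everyone had a year of follow-up.

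**What to change.** Reconcile the Table 6 footnote with sections 5.8, 8.1.2.1, 8.1.5.6 and 8.2, and align the wording of section 3.1. State one post-treatment collection window for AEs and one for SAEs, applying to every patient who starts pembrolizumab, whatever the reason for stopping. Say whether collection ends or is only flagged when new anti-cancer therapy begins; section 8.1.5.6 currently uses that as an end point. The 3-monthly follow-up visits (section 8.1.5.7) and the 12-weekly record review after progression (section 8.1.5.8) already provide the contacts. Flag events that follow new therapy.

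If the windows are left as they are, add to section 9.4 that headline incidence, and any time-to-first-event analysis, uses the window common to all patients: 30 days after the last dose for AEs and 90 days for SAEs. Report completers' later events separately. This makes the incidence comparable across patients but not complete for late non-serious events.

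The cost of the first option is protocol wording, some additional AE entries and harder attribution after new therapy. The second needs no new data.
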